This study will be a prospective cohort study, in which we will evaluate two methods of evaluating intraoperative blood loss during cesarean delivery (usual clinical assessment versus Device). Of note, the subjects consented will be used as self-controls.

- 2. Summary of project:** This study will be a prospective cohort study. Patients who are scheduled for an elective cesarean and meet criteria for inclusion in the study will be approached for participation at same day of admission. Written informed consent will be obtained from the patients by the Co-PI ([name]) and by the study collaborators ([name],

[name], [name], [name], and [name]). If patients agree to participate, a CBC (complete blood count) will be obtained via venous puncture. The device will be used during the delivery in the operating room. The device will be used to assess EBL by the research staff only and results/ EBL assessment will be masked to the clinical team. Unmasking will only occur after collecting the data from the device with purpose to perform data analysis. Patient management will be according to the clinical team. All patients undergo a CBC postpartum. The drop in Hgb (Δ Hgb) between the pre and post cesarean CBCs will be calculated for each patient. Patients will be divided into quartiles of Δ Hgb. Cases will be those patients whose Δ Hgb is in the upper quartile, while controls will be those patients whose Δ Hgb is in the lower 3 quartiles. We will be comparing EBL by standard clinical assessment versus result from the device between cases and controls.

The colorimetric Triton system which comprises of the device, software analysis and staff training will be supplied by the manufacturer free of charge. We will be offering our skills, fellows and residents, who will be collecting data and we will be performing the data analysis. Results will be available to the manufacturer after results are completed. The results of this study will be presented in conferences or published in a peer-review journal.

Demographic information will be obtained from the electronic medical record. The data will be kept on a password secured UTMB computer. An encrypted USB flash drive will be used to transfer data. The data will be identified and linked to the patient using the medical record number (MRN). During data analysis, all patient identifiers will be deleted.

3. Study procedures: VISIT#1

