3.7 Outcomes

- **Primary outcome:** Differences in EBL between cases and controls using clinical estimate versus device assessment.
- **Secondary outcomes: System performance (ROC sensitivity analysis and correlation).** Delta hemoglobin, transfusion requirements, administration of uterotonics, colloid resuscitation, post-partum hemorrhage or hemorrhagic shock.

4. Criteria for inclusion of subjects:

Pregnant women between the ages of 18-50.
Scheduled cesarean delivery.

5. Criteria for exclusion of subjects:

- Incarcerated patients
- Patient unwilling or unable to provide consent
- Intrauterine fetal demise (no fetal heart beat identified and documented by two physicians)
- Placenta previa or other known placental anomalies
- Enrolled in another trial that may affect outcome.

6. Sources of research material: Electronic medical records.

7. Recruitment methods and consenting process: See 3.1 above.

8. Potential risks

8.1 Loss of confidentiality: Any time information is collected, there is a potential risk for loss of confidentiality. Every effort will be made to keep the subject's information confidential; however, this cannot be guaranteed.

9. Potential benefits: With this novel approach of assessing blood loss more objectively during cesarean section, there are many potential benefits,

including: decrease in the delay in diagnosis of hemorrhagic shock, decrease in delay in interventions and improved postpartum surveillance. In addition, this data will be useful in designing a level 1 trial to measure outcomes such as transfusion rates, transfusion complications, hemorrhage and maternal death.

10. Data monitoring: The PI, research coordinator, and collaborators will ensure that all aspects of data quality adhere to the study design. This will include monitoring for adherence to consent procedures, inclusion and exclusion criteria, valid abstraction, correct entry, timeliness and responsiveness to data queries. Data will be collected and stored with the participant ID code only. The master enrollment log linking patient identifiers with study ID numbers will be kept in a password protected database on the Ob/Gyn department's internal server. Several data collection forms will be used. Data on these forms will be devoid of personal identifiers and will be securely stored at the division offices. The research coordinator will be available to monitor the data and correct any discrepancies based on source documents if needed.

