11. Procedures to maintain confidentiality: Each subject will be assigned a study number with personally identifiable information deleted or removed. If needed, charts will be reviewed in the medical records area. Subjects' information will be de-identified and tagged with a number. Data will be collected and stored on a UTMB password-protected computer.

Statistical approach: We will be performing a prospective study. After defining cases and controls using the cutoff of upper quartile for pre- to postop- hemoglobin drop. We will use univariable and multivariable analysis to check for association between both blood loss assessment techniques using the device and the subjective clinical assessment among our cases and controls. We will be comparing cases versus controls (two groups) and EBL (continuous variable and primary outcome) hence t tests/means were used for our sample calculation; For the purpose of the study, we believe a sample size of 220 will be able to evaluate our primary outcome. Accounting for 10% loss of data or follow-up: **N total is 242 subjects**. This was based on a study of 50 patients having cesarean deliveries using the Triton System (the mean measured blood loss was 555.8 ml with a standard deviation of 317 ml (11). For a power of 80% and alpha of 0.05 and 25% effect size 1: 3 allocation (25%ile versus 75%ile PP delta hemoglobin):

Estimated sample sizes for a two-sample means test
t test assuming $sd_1 = sd_2 = sd$
 $H_0: \mu_2 = \mu_1$ versus $H_a: \mu_2 \neq \mu_1$

Study parameters:

alpha = 0.0500
power = 0.8000
delta = -139.0000
m1 = 555.0000
m2 = 416.0000
sd = 317.0000
N2/N1 = 3.0000

Estimated sample sizes:

N = 220
N1 = 55
N2 = 165

We will also be using multiple model correlation (Pearson correlation coefficient) (secondary outcome) between EBL Device and EBL Standard. We will also perform ROC curve analysis (secondary outcome) to compare the area under the curve (AUC) to predict Δ Hgb in the upper quartile by clinical estimate versus device assessment. The coefficient of multiple correlation takes values between 0 and 1; a higher value indicates a better predictability of the dependent variable (EBL Device) from the independent variable (EBL standard).

REFERENCES

1. AbouZahr, C. (2003). Global burden of maternal death and disability. *Br Med Bull*, 67, 1-11.
2. Chesley, L. C. (1972). Plasma and red cell volumes during pregnancy. *Am J Obstet Gynecol*, 112(3), 440-450.

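### The two system-performance measures, Pearson r and AUC, cannot show how many mL device and clinical EBL differ by in the same woman, and no paired difference or limits of agreement is specified

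*Combined protocol and SAP*

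**What the plan says.** Section 3.7 (Outcomes) opens the secondary outcomes with "System performance (ROC sensitivity analysis and correlation". The Statistical approach paragraph, after section 11, fills this in:

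- Correlation: "We will also be using multiple model correlation (Pearson correlation coefficient) (secondary outcome) between EBL Device and EBL Standard". It adds "The coefficient of multiple correlation takes values between 0 and 1" and that "a higher value indicates a better predictability of the dependent variable (EBL Device) from the independent variable (EBL standard".
- ROC: "We will also perform ROC curve analysis (secondary outcome) to compare the area under the curve (AUC) to predict" a hemoglobin drop in the upper quartile, by clinical estimate against device.
- Modelling: "univariable and multivariable analysis to check for association between both blood loss assessment techniques" among cases and controls. No model is written down.

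The primary outcome in section 3.7 is "Differences in EBL between cases and controls using clinical estimate versus device assessment". The sample-size calculation treats it as a two-sample t test of cases against controls. The end of section 1 says "Of note, the subjects consented will be used as self-controls", so both readings exist for each woman. The document names no paired difference, limits of agreement, concordance coefficient, slope or intercept.

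**The concern.** The study's title is about validating a method of measuring a volume. A reader of the results will want to know how far the device and the usual estimate are apart in the same patient, and how variable that gap is. The two measures filed under system performance cannot say. Pearson r is blind to offset and scale. AUC depends only on the ordering of patients within each method, so it is blind to both as well.

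Section 1 gives the question practical weight. It says that visual estimates tend to run low, and it cites a loss above 1,000 mL at cesarean as a common definition of postpartum hemorrhage. Whether two methods put a woman on the same side of a fixed mL line depends on their mL difference, which r and AUC leave out. Section 2 makes every patient a matched pair, so the information is collected but no analysis is assigned to it.

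There is also a wording slip. The plan equates Pearson r, which runs from -1 to 1, with a coefficient of multiple correlation, which runs from 0 to 1.

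**Working it through.** **Inputs from the Statistical approach paragraph:** means 555 and 416 mL, SD 317 mL, 55 cases and 165 controls, two-sided alpha 0.05, power 80%. **Assumed, not in the documents:** the clinical SD, the device-clinical r, and the rescaling factors 0.75 and 0.5, which are illustrations only.

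**1. The plan's own figure.** A two-sample t test with difference 139 mL, SD 317 mL and 1:3 allocation has noncentral-t power 0.8006 at 55 + 165 and 0.793 at 54 + 162. N = 220 is reproduced.

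**2. What r, AUC and t miss.** Overall mean = (55 × 555 + 165 × 416)/220 = 450.75 mL. Let clinical EBL have the device's mean and SD, then multiply it by 1, 0.75 or 0.5. At any r, the correlation and the clinical AUC do not move. For the clinical case-control t, sqrt(1/55 + 1/165) = 0.1557:

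| Factor | Case-control difference | SD | t | Mean device minus clinical |
|---|---|---|---|---|
| 1 | 139 mL | 317 mL | 139/(317 × 0.1557) = 2.82 | 0 mL |
| 0.75 | 104.25 mL | 237.75 mL | 2.82 | 0.25 × 450.75 = 113 mL |
| 0.5 | 69.5 mL | 158.5 mL | 2.82 | 0.5 × 450.75 = 225 mL |

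**3. What the primary analysis would still show.** At factor 0.5 the clinical group means are 277.5 and 208 mL, against 555 and 416 mL by device. The clinical overall mean is (55 × 277.5 + 165 × 208)/220 = 225.4 mL, and 450.75 - 225.4 = 225 mL. With complete pairs this equals the mean paired difference, so an average gap is visible once means are tabulated by method.

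**4. What remains unspecified.** Group means do not show patient-level spread. With equal means and both SDs 317 mL, the SD of the paired difference is SDd = 317 × sqrt(2(1 - r)), and the limits of agreement are ±1.96 × SDd:

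- r = 0.3: SDd 375.1 mL, limits ±735 mL
- r = 0.5: SDd 317.0 mL, limits ±621 mL
- r = 0.7: SDd 245.5 mL, limits ±481 mL

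Nor does r alone fix the spread. Holding r at 0.7 and the means equal, a clinical SD of 0.5 or 1.5 times 317 mL gives ±461 or ±666 mL.

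**5. Could the association analysis fill the gap?** Suppose it is a regression of device on clinical EBL, with r = 0.5. With no mL bias, the slope is 0.5 and the intercept is 450.75 - 0.5 × 450.75 = 225 mL. With clinical EBL halved, the slope is 0.5 × 317/158.5 = 1.0 and the intercept is 450.75 - 1.0 × 225.4 = 225 mL. The slope nearest 1 belongs to the biased case, and the intercept does not separate the two. A regression is no substitute for the paired difference.

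**6. Precision of the missing analysis, 220 pairs, both SDs 317 mL.** The CI half-width for the mean difference is 1.971 × SDd/sqrt(220). The SE of each limit is approximately SDd × sqrt(3/220).

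| r | CI half-width | SE of a limit |
|---|---|---|
| 0.3 | 49.8 mL | 43.8 mL |
| 0.5 | 42.1 mL | 37.0 mL |
| 0.7 | 32.6 mL | 28.7 mL |

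These rest on equal SDs. If the clinical SD were 158.5 mL and r = 0.5, SDd = sqrt(317² + 158.5² - 2 × 0.5 × 317 × 158.5) = 274.5 mL and the half-width is 1.971 × 274.5/sqrt(220) = 36.5 mL.

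**The case against.** The strongest reply is that nothing planned is invalid. The plan reads r as predictability and does not call it agreement. Ranking of the methods goes to the AUC comparison against hemoglobin drop, which is a suitable place for it. The primary analysis works in mL and rests on means, so a 225 mL average gap would not stay hidden (step 3). If both overall SDs were also reported, a reader could reconstruct the limits of agreement from them and r. All of this stands. It narrows the point to an unspecified paired interval and spread; the plan does not commit to reporting those SDs.

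A reader might be tempted further:

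- *That r is wrongly used to decide which method is better.* It is true that r is symmetric and cannot do so, but the plan does not ask it to. Limits of agreement would not rank the methods either.
- *That the study cannot detect an mL bias.* Step 3 shows otherwise for the average.
- *That the postpartum hemorrhage outcome is compromised.* Section 3.7 lists it without saying how it is defined or by which method, so the link to the 1,000 mL line is only an inference.

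Two further objections shape the remedy. Section 1 calls estimates at delivery notoriously inaccurate, so agreement with the clinical estimate cannot by itself validate the device. Section 1 also describes the device as imaging sponges, while the traditional estimate uses drape blood as well as a sponge count. The documents do not say whether the device total includes blood outside the sponges. If it does not, part of any paired difference reflects different blood sources.

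**Conclusion.** The point holds in this limited form. The two measures named as system performance cannot show the within-patient mL difference. Group means would give its average, but no paired confidence interval or patient-level spread is specified, although the paired data are being collected. The planned number of patients would estimate the mean difference to within about ±50 to ±33 mL, assuming 220 complete pairs, both SDs of 317 mL and r of 0.3 to 0.7. Only a secondary outcome is affected. The primary conclusion, N = 220 (242 with allowance for loss) and the AUC comparison are unchanged. It is worth making because the study is presented as a validation and the remedy is nearly free.

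**What to change.** - Keep the AUC comparison as planned.
- Report the device-clinical correlation as descriptive association, and call it Pearson r (range -1 to 1), not a multiple correlation.
- Add the paired mean difference, device minus clinical EBL, with 95% CI, and Bland-Altman 95% limits of agreement. Use the log or ratio scale if the spread grows with volume.
- Label these as agreement, not accuracy, because clinical EBL is not a reference standard.
- State which blood sources (sponges, drape, suction) each total covers, so that a difference in source is not read as disagreement between methods.
- Say what the association analysis is. If it is a regression of device on clinical EBL, report slope and intercept alongside the paired difference, not in its place.
- Optionally, cross-classify the two methods in the same women at 1,000 mL.

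The cost is some SAP wording and a little extra analysis. Both EBL readings are already collected, so no new measurements and no change to N are needed.
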